10.1 General Considerations

Safety parameters will be evaluated for the safety analysis set by treatment group.

10.2 Adverse Events

Adverse events (AEs) will be classified according to the Medical Dictionary for Regulatory Activities (MedDRA) version 17.1 or later.

Written narratives will be issued for all serious AEs (including deaths) and AEs leading to discontinuation.

A 'pre-treatment' AE will be defined as an AE that occurs between screening and the first dose of the IMP. A 'treatment-emergent AE (TEAE)' will be an AE which occurs in the time interval from initial dosing (IMP intake) to the end of treatment visit. If an AE on Day 1 occurs before IMP intake, it will be recorded as a pre-treatment AE.

If causality is missing, the AE will be regarded as being reasonably possibly related to IMP. Related AEs (judged as being reasonably possibly related to IMP) will be termed adverse drug reactions (ADR).

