Safety: The safety analyses will be based on all subjects who receive at least 1 dose of IMP. All adverse events will be coded by system organ class and preferred term using the most current version of the Medical Dictionary for Regulatory Activities (MedDRA). A treatment-emergent adverse event will be defined as any adverse event occurring after the start of IMP or pre-existing medical condition that worsens in intensity after the start of IMP.

Clinical laboratory variables will be presented in 2 ways. First, mean change from baseline to the end of the double-blind treatment visit will be summarized. Baseline will be defined as the last assessment before the first dose of IMP. Second, the number and percentage of subjects with treatment-emergent potentially clinically significant laboratory values on or before the end of the double-blind treatment visit will be tabulated.

Other safety assessments will also be summarized descriptively.

TABLE OF CONTENTS

SYNOPSIS	2
LIST OF TABLES	12
LIST OF FIGURES	12
LIST OF ABBREVIATIONS AND DEFINITION OF TERMS	13
1 INTRODUCTION	16
1.1 Background	16
1.2 Scientific Justification for Conducting the Trial	17
1.3 Benefit / Risk Aspects	17
2 TRIAL OBJECTIVES AND ENDPOINTS	18
2.1 Objectives	18
2.2 Endpoints	18
3 INVESTIGATIONAL PLAN	20
3.1 Overall Trial Design	20
3.1.1 Overall Design and Control Methods	20
3.1.2 Trial Design Diagram	21
3.1.3 Trial Schedule	23
3.2 Planned Number of Trial Sites and Subjects	23
3.3 Interim Analysis	23
3.4 Data Monitoring Committee	23
3.5 Discussion of Overall Trial Design and Choice of Control Groups	23
3.5.1 Trial Design	23
3.5.2 Selection of Endpoints	23
3.5.3 Blinding	23
3.5.4 Selection of Doses in the Trial	23
3.5.5 Selection and Timing of Dose for Each Subject	24
3.5.6 Selection of Trial Population	24
3.5.7 Withdrawal Criteria	24
3.5.8 Follow-up Procedures	24
4 SELECTION OF TRIAL POPULATION	25
4.1 Trial Population	25
4.1.1 Inclusion Criteria	25
4.1.2 Exclusion Criteria	25
4.2 Method of Assigning Subjects to Treatment Groups	26
4.3 Restrictions	26
4.3.1 Prior and Concomitant Therapies	26
4.3.2 Prohibited Therapy	27
4.3.3 Other Restrictions	27
4.4 Withdrawal Criteria	27
5 TREATMENTS	29
5.1 Treatments Administered	29
5.1.1 Investigational Medicinal Product (IMP)	29
5.1.2 Non-Investigational Medicinal Product (NIMP)	29
5.2 Characteristics and Source of Supply	29

5.3	Packaging and Labelling.....	29
5.4	Conditions for Storage and Use	29
5.5	Blinding / Unblinding	29
5.5.1	Blinding.....	29

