- e For females of childbearing age or <1 year postmenopausal; if positive, the subject will not be enrolled in the trial. A serum pregnancy test will be performed at Visit 0 (screening) for Pathway 3 – *de novo* only. Urine pregnancy tests will be performed for all subjects at Visit 1 (baseline/Day 0) and Visit 5 (Month 6) or early withdrawal.
- f If positive for blood, leucocytes, or nitrite, perform microscopic urinalysis.
- g Results must be available at randomization (Visit 1).
- h For all subjects; Study 000174 end-of-treatment Clinical and Endoscopic Response Score assessments will be utilized for Pathways 1 and 2 only.
- i Baseline flexible sigmoidoscopy/colonoscopy for Pathway 3 – *de novo* subjects will be scheduled at screening (Visit 0) and completed at least 4 days prior to randomization (Visit 1) to allow sufficient time for the central reading.
- j Adverse events are collected from the signing of informed consent.
- k Subject daily diary data will be collected electronically and daily diary compliance will be assessed.
- l IMP to be distributed at Day 0, and will be taken the following day (Day 1).
- m No coagulation panel.
- n Subjects will bring IMP kit to site for assessment of compliance; this same kit will be used until Visit 3.

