8.2.2 Recording of Adverse Events

The investigator must record all AEs in the AE log provided in each subject's eCRF with information about:

- AE
- date and time of onset (time can be omitted, if applicable)
- intensity
- causal relationship to IMP

- action taken to IMP
- other action taken
- date and time of outcome (time can be omitted, if applicable)
- outcome
- seriousness

Each of the items in the AE log is described in detail in the following sections.

Adverse Events

Adverse events should be recorded as diagnoses, if available. If not, separate signs and symptoms should be recorded. One diagnosis/symptom should be entered per record.

If a subject suffers from the same AE more than once and the subject recovers between the events, the AEs should be recorded separately. If an AE changes in intensity, a worst-case approach should be used when recording the event, i.e. the highest intensity and the longest duration of the event.^a

A procedure is not an AE; the reason for conducting the procedure is. Hospitalization is not an AE; the reason for hospitalization is. Death is not an AE, but the cause of death is (an exception is sudden death of unknown cause, which is an AE).

Date and Time of Onset

The date of onset is the date when the first sign(s) or symptom(s) were first noted. If the AE is an abnormal clinically significant laboratory test or outcome of an examination, the onset date is the date the sample was taken or the examination was performed.

Intensity

The intensity of an AE must be classified using the following 3-point scale:

Mild: awareness of signs or symptoms, but no disruption of usual activity

Moderate: event sufficient to affect usual activity (disturbing)

Severe: inability to work or perform usual activities (unacceptable)

^a Exception: if an AE with onset before the first IMP administration (i.e., a pre-treatment AE) changes in intensity, this must be recorded as 2 separate events. The initial AE should be recorded with outcome “not yet recovered” and the date and time of outcome are when the intensity changed. The second AE should be recorded with date and time of onset when the intensity changed.

Causal Relationship to IMP

The possibility of whether the IMP caused the AE must be classified as 1 of the following:

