9.8.2 Adverse Events

A ‘pre-treatment’ AE will be defined as an AE that occurs between screening and the first dose of the IMP. A ‘treatment-emergent AE (TEAE)’ will be an AE that occurs in the time interval from initial dosing (IMP intake) to the end of treatment visit. If an AE on Day 1 occurs before IMP intake, it will be recorded as a pre-treatment AE.

Written narratives will be issued for all SAEs and AEs leading to withdrawal. If causality is missing, the AE will be regarded as being reasonably possibly related to IMP. Related AEs (judged as being reasonably possibly related to IMP) will be termed adverse drug reactions (ADR).

An AE overview summary table will be prepared for the safety analysis population. It will display the number and percentage of subjects reporting an AE and the number of events reported for each treatment group. The following categories will be displayed:

- any TEAEs
- deaths
- SAEs
- AEs leading to discontinuation
- severe AEs
- ADRs

Number and percentage of subjects reporting the following types of TEAEs will be summarized by MedDRA SOC (alphabetically) and PT (in decreasing frequency of occurrence):

- any TEAEs
- common TEAEs
- causal relationship to IMP with reasonable possibility or no reasonable possibility
- intensity with mild, moderate, or severe
- AEs leading to death
- SAEs
- AEs leading to discontinuation

Supporting data listings will be provided for:

- all AEs sorted by trial site and subject ID
- all AEs sorted by MedDRA SOC and PT
- SAEs
- AEs leading to death
- AEs leading to discontinuation

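### A pre-treatment AE that only steps down in intensity after the first dose is counted as treatment-emergent, because the TEAE rule looks at timing alone

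*SAP*

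**What the plan says.** Three rules bear on this point.

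**Classification.** In SAP section 10.2 a TEAE "will be an AE which occurs in the time interval from initial dosing (IMP intake) to the end of treatment visit". Protocol section 9.8.2 says the same: it "will be an AE that occurs in the time interval from initial dosing (IMP intake) to the end of treatment visit". The complementary class is also set by timing: a pre-treatment "AE will be defined as an AE that occurs between screening and the first dose of the IMP". Neither section compares intensity before and after the first dose.

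**Recording.** The general rule in protocol section 8.2.2 is: "If an AE changes in intensity, a worst-case approach should be used when recording the event". That gives one record, at the highest intensity. Footnote a makes an exception for an AE that began before the first IMP administration. If such an AE "changes in intensity, this must be recorded as 2 separate events". It continues: "The second AE should be recorded with date and time of onset when the intensity changed". The initial record is closed on the same date. The trigger is any change, not only a worsening.

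**Synopsis.** The safety paragraph of the protocol synopsis has a TEAE definition with two limbs: any AE occurring after the start of IMP, or a "pre-existing medical condition that worsens in intensity after the start of IMP". The second limb appears in neither protocol section 9.8.2 nor the SAP. SAP section 12 declares no deviation from the protocol's planned analysis.

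**The concern.** The usual purpose of splitting a pre-treatment AE is to let a worsening on treatment be seen as a new event. Here the split happens in both directions, and the classification rule has no filter to remove the downward half. An event that began before dosing and then eased is tabulated as if it had emerged on treatment.

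Incidence and severity of AEs is the last of the listed secondary endpoints. The records concerned would enter the any-TEAE row of the overview table (SAP section 10.2.1) and the tables by SOC and preferred term, intensity and causality (SAP section 10.2.2). They would also count as adverse drug reactions if the investigator judged them related, or if causality was missing, since SAP section 10.2 treats missing causality as related.

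**Working it through.** The plan attaches no figure to this point, so the check is one of logic: pass each possible record through the recording rule and then through the classification rule.

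**Step 1: can pre-treatment AEs exist in the database?** Yes. Note j to the flow chart in protocol section 6.1 says: "Adverse events are collected from the signing of informed consent". Pathway 3 subjects are screened up to 21 days before first dose. Pathways 1 and 2 consent at Visit 1 (Day 0) and take the first dose on Day 1, so they have about one day.

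**Step 2: an illustrative record.** A moderate headache starts on Day -3, eases to mild on Day 2 and resolves on Day 4.
- Footnote a gives record 1 (moderate, Day -3 to Day 2) and record 2 (mild, onset Day 2, resolved Day 4).
- Record 2 starts after first dose on Day 1, so it meets the TEAE rule and fails the pre-treatment rule.
- If the same headache had stayed moderate and resolved on Day 4, there would be one record with onset Day -3, and no TEAE.
- If it had first started on Day 2 as moderate and then eased, the worst-case rule would give one record, moderate.

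So two subjects with the same pre-dose headache are classified differently, and the one whose headache eased in stages is the one with a TEAE.

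**Step 3: all changes on the three-point scale (mild, moderate, severe) between first dose and the end-of-treatment visit.**

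| Before first dose | After first dose | TEAE by timing rule | TEAE if worsening is required |
|---|---|---|---|
| mild | moderate | yes | yes |
| mild | severe | yes | yes |
| moderate | severe | yes | yes |
| severe | moderate | yes | no |
| severe | mild | yes | no |
| moderate | mild | yes | no |

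The timing rule admits 6 of 6. A worsening condition keeps 3 and drops the 3 step-downs.

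**Step 4: what lies outside the problem.** Recovery is an outcome, not an intensity category, so resolution alone creates no second record. A mild AE cannot step down. A change before first dose gives a second record that is still pre-treatment.

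**Step 5: which tables can move.** A record that only steps down is at most moderate, so the severe TEAE row is not inflated. For the common-TEAE table (at least 2% in any arm, SAP section 10.2.2), assume all 130 planned subjects per arm are dosed: 0.02 x 130 = 2.6. Three subjects reach the threshold (3/130 = 2.3%) and two do not (2/130 = 1.5%). For step-downs alone to put a term in that table, three subjects in the same arm would need the same preferred term.

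**The case against.** The strongest reply is that the affected pool is narrow and the consequences slight. Most of that stands.

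- Protocol section 8.1 sends findings from screening assessments and examinations to medical history, so they are not AEs at all.
- The Pathway 3 endoscopy must be complete at least 4 days before randomization, and first dose is the day after. An AE from bowel preparation or endoscopy would have to last at least 4 + 1 = 5 days and only then step down.
- Causality is assessed record by record, so an easing pre-dose event need not become an adverse drug reaction.
- AE summaries are descriptive, with no planned test between arms, and the listings keep both records of a pair visible.

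A second reply is that the SAP agrees with protocol section 9.8.2. That is true: the gap is shared by both documents and is not a SAP departure from the protocol body. A reader might also infer that the synopsis settles the intent against counting these records. It does not do so cleanly. Its first limb, read literally, could admit the split record too, and its second limb speaks of a pre-existing condition rather than of a split AE.

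A reader might try to put a number on the effect. For example, assume that Pathway 3 is 40–80% of 260 subjects, that 5–15% of these have an AE ongoing at first dose, and that 30–60% of those step down. The low end is 260 x 0.4 x 0.05 x 0.3 = 1.6 records and the high end 260 x 0.8 x 0.15 x 0.6 = 18.7. None of the three shares is in the documents, and the twelvefold spread reflects only the guesses, so no count is claimed here.

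None of these replies removes the misclassification. No other text in either document excludes a stepped-down record from the TEAE class.

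**Conclusion.** The point holds as a minor definitional error. Applied literally, footnote a and the timing-only rule count a pre-treatment AE that steps down after first dose as treatment-emergent, in three of the six possible intensity changes. This reads the SAP's rule as applying to each record's onset date. That is the natural reading, since footnote a sets the second record's onset at the change.

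The effect is on descriptive counts: any TEAE, TEAEs of mild or moderate intensity, the causality table, and adverse drug reactions where the record is judged related or causality is missing. It is probably small, and its size cannot be derived from the documents. A reader might infer that every improving or resolving pre-treatment AE is miscounted, or that the rule favours one arm. The documents support neither: only a step down on the scale creates a record, and the rule works without regard to treatment. The efficacy analyses are untouched.

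**What to change.** In SAP section 10.2, and in protocol section 9.8.2 aligned with the synopsis, define a TEAE as an AE with first onset on or after the first dose of IMP, or a pre-treatment AE whose intensity after the first dose exceeds its intensity before it. Then state explicitly that the second record created under footnote a of protocol section 8.2.2 is a TEAE only if its intensity is higher than that of the initial record, and otherwise stays with the pre-treatment AE. The explicit statement is needed because copying the synopsis wording alone would leave its first limb open to the same reading.

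The cost is one sentence in the text. Programming must link the paired records by subject, term and date; the initial record's outcome date equals the second record's onset date. No new data are collected.

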10.2.1 Overview of Treatment-Emergent Adverse Events

An AE overview summary table will be prepared including the number of subjects reporting an AE, the percentage of subjects (%) with an AE, and the number of events (E) reported, for the following categories:

- Any TEAEs
- Deaths
- Serious adverse events
- Adverse events leading to discontinuation
- Severe TEAEs
- Adverse drug reactions

10.2.2 Incidence of Adverse Events

The summaries will include the total number of subjects reporting an AE, the percentage of subjects (%) with an AE, and the number of events (E) reported. AEs will be presented by SOC sorted alphabetically and PT sorted in decreasing frequency of occurrence.

Summary tables will be prepared for:

- Any TEAEs
- Common TEAEs, defined as TEAEs with an incidence $\geq 2\%$ of subjects in any treatment group
- Any TEAEs by causality (related/unrelated)

- Any TEAEs by intensity
- Any AEs leading to death
- Serious adverse events
- Any TEAEs leading to discontinuation

Supporting data listings will be provided for:

- All adverse events sorted by trial site and subject ID
- All adverse events sorted by MedDRA SOC and PT
- Serious adverse events
- Adverse events leading to death
- Adverse events leading to discontinuation

A listing of SOC and PT for all unique verbatim will be provided.

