3.2 Planned Number of Trial Sites and Subjects

This trial will be conducted at approximately 110 sites in North America and Europe. Approximately 260 subjects will be randomized to receive mesalamine 2 g extended release granules (sachet) or matching placebo in a 1:1 ratio (130/treatment regimen).

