4.4 Withdrawal Criteria

Subjects have the right to withdraw from the trial at any time for any reason, without the need to justify their decision. However, the investigator should record the reason for the subject's withdrawal. The investigator also has the right to withdraw subjects.

Subjects will be withdrawn in the following cases:

- pregnancy at any time during the trial will be a reason for withdrawal
- withdrawal of consent
- worsening of UC with a need for an escalation of the therapy (i.e., surgical therapy, use of steroids, immunosuppressive or immunomodulating drugs, biologics, increase dose of 5-ASA in any form)
- request for termination of the trial by regulatory authorities or sponsor
- the subject develops any AE that, in the opinion of the investigator, warrants the subject's withdrawal from treatment. An AE form will be completed as appropriate, and the subject will be followed until the event is clinically stable.

For subjects who discontinue due to an AE, all efforts will be made to follow the outcome of the AE and to assess the efficacy criteria.

For any discontinuation, the investigator will obtain all the required details and document the date of the premature termination and the main reason in the electronic case report form (eCRF). Since an excessive rate of withdrawals can render the trial devoid of meaning, the unnecessary withdrawal of subjects should be avoided.

Subjects who withdrew from the trial will not be replaced.

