3.2 Determination of Sample Size

The true remission rates at Month 6 for mesalamine 2 g extended release granules (sachet) and placebo regimens were assumed as 68% and 49%, respectively, based on The mesalamine Study Group (1996)(3), Hawkey et al (1997)(4), and Apriso™ package insert (2009)(5). Under these assumptions, a sample size of 120 randomized subjects per group will provide at least 85% power to detect a statistically significant treatment group difference in the remission rate at a two-sided 0.05 significance level using the chi-square test. To maintain the power for the primary efficacy analysis that excludes subjects who are rolled over from the placebo group in the 000174 trial via Pathway 1, approximately 260 subjects will be randomized.

4 Subject Disposition

The number of screened subjects will be summarized, and for subjects not randomized, the primary reason for exclusion from randomization will be summarized.

The number and percentage of subjects who are randomized, are treated with IMP, prematurely discontinued, and completed the trial will be summarized with the reason of premature discontinuations.

The time to discontinuation will be summarized by the Kaplan-Meier estimates, and the treatment group difference will be tested by the log-rank test. In addition, reason-specific discontinuation will be summarized by the cumulative incidence estimates.

5 Protocol Deviations

The following protocol deviations will be identified as major protocol deviations:

- Overall IMP compliance of less than 80%
- Not taking the randomized IMP
- Taking prohibited medications

The final definition of major protocol deviations will be determined prior to breaking the blind.

The number and percentage of subjects with protocol deviations will be summarized.

6 Analysis sets

For each analysis set, the number and percentage of subjects excluded from it will be summarized by the reason of the exclusion.

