8.1 Extent of Exposure

The length of the treatment, calculated as (last dose date – first dose date + 1), will be summarized by treatment group for the safety analysis set.

Following categorical summaries will be made:

- < 14 days, 14 - < 28 days, 28 - <56 days, 56 - <84 days, 84 - <112 days, 112 - <140 days, 140 - <168 days, and 168 days or more
- At least 1 day, at least 14 days, at least 28 days, at least 56 days, at least 84 days, at least 112 days, at least 140 days, and at least 168 days

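### AE tables use crude percentages and counts only, although relapse ends observation early; add person-time rates, shown with and without UC worsening

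*SAP*

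**What the plan says.** SAP 10.2.1 and 10.2.2 report, by arm, the number of subjects with an AE, "the percentage of subjects (%) with an AE, and the number of events (E) reported". Protocol 9.8.2 plans the same measures. The denominator is the safety set, meaning everyone with at least one dose (SAP 6.5). No person-time rate, time-to-first-AE analysis or cumulative incidence of AEs is planned in either document.

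Four other provisions bear on this:

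- **Withdrawal.** Protocol 4.4 lists "worsening of UC with a need for an escalation of the therapy" as a reason for withdrawal.
- **AE window.** Under SAP 10.2 a TEAE is one that "occurs in the time interval from initial dosing (IMP intake) to the end of treatment visit". The note to the schedule of procedures has subjects who stop treatment complete the end-of-treatment assessments, and that visit doubles as the early-withdrawal visit. Protocol 3.5.8 plans no further follow-up after participation.
- **Exposure.** SAP 8.1 computes length of treatment from first to last dose, and it "will be summarized by treatment group for the safety analysis set". SAP section 4 gives Kaplan-Meier curves, a log-rank test and reason-specific cumulative incidence for discontinuation. Neither is linked to the AE tables.
- **AE definition.** Protocol 8.1 counts the reason for a change in medication as an AE and does not exempt UC worsening.

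**The concern.** In a maintenance trial, relapse ends both treatment and AE observation. If the drug prevents relapse, the placebo arm is observed for less time because the drug works. A crude percentage over everyone dosed then gives the longer-observed arm more opportunity to record headache, nausea, infection or any other event unrelated to relapse. The incidence of AEs is a stated secondary objective and endpoint, and descriptive tables by arm are read as comparisons. At stake is whether a small excess on mesalamine in the non-UC rows reflects the drug or only extra time at risk.

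**Working it through.** **The plan's own figure.** SAP 3.2 states that the rates for mesalamine and "placebo regimens were assumed as 68% and 49%, respectively", and that "a sample size of 120 randomized subjects per group will provide at least 85% power" (two-sided 0.05, chi-square). With pooled variance under the null:

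n = [1.96·√(2·0.585·0.415) + 1.036·√(0.68·0.32 + 0.49·0.51)]² / 0.19² ≈ 119.2, so 120 per arm, with power 85.2%. The figure reproduces. The documents state no AE or exposure figure to check.

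**Inputs.** From the documents: non-remission of 32% (mesalamine) and 51% (placebo), and 168 days of planned follow-up. Assumed, because the documents do not give them:

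- a share f of Month 6 non-remitters withdraws early, with f from 0 to 1 and a constant withdrawal hazard;
- the risk of a non-relapse AE over a full 168 days is 20%, 40% or 60%, with the same hazard in both arms.

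**Formulas.**

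- Early withdrawal: q = f·(1 − remission)
- Withdrawal hazard: h = −ln(1 − q)/168
- Mean observed time: q/h
- AE hazard: λ = −ln(1 − risk)/168
- Crude AE percentage: λ/(λ + h)·[1 − exp(−(λ + h)·168)]

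For example, at f = 1 on placebo q = 0.51, h = 0.713/168 = 0.00425 and mean time = 0.51/0.00425 = 120 days.

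**Results at 40% full-period risk (mesalamine / placebo).**

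| f | Withdrawn early | Mean days observed | Time ratio | Crude AE % | Excess (points) |
|---|---|---|---|---|---|
| 0 | 0% / 0% | 168 / 168 | 1.00 | 40.0 / 40.0 | 0.0 |
| 0.25 | 8.0% / 12.8% | 161.2 / 157.0 | 1.03 | 38.5 / 37.6 | 0.9 |
| 0.5 | 16.0% / 25.5% | 154.2 / 145.5 | 1.06 | 37.0 / 35.1 | 1.9 |
| 0.75 | 24.0% / 38.3% | 146.9 / 133.3 | 1.10 | 35.4 / 32.4 | 3.0 |
| 1 | 32.0% / 51.0% | 139.4 / 120.1 | 1.16 | 33.7 / 29.5 | 4.3 |

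Excesses are taken before rounding. For f from 0.25 to 1 the excess is 0.5 to 2.2 points at 20% risk and 1.3 to 6.0 points at 60% risk. Event counts inflate by the time ratio. Timing matters too: if every non-remitter left on day 28, mean time would be 123.2 against 96.6 days, a ratio of 1.28. Events or first events per person-time have a ratio of 1.00 in every row by construction.

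**Relapse recorded as an AE.** Let a share g of the early withdrawals be recorded as AEs. At 40% risk and f = 0.5, the any-TEAE difference (mesalamine minus placebo) is +1.9 points at g = 0, zero at g = 0.25 and −5.7 points at g = 1 (49.6% vs 55.3%). At f = 1 it is +4.3, +0.4 and −11.4. The sign therefore changes at about 25%.

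A second model, with withdrawal times uniform over 168 days and 30% full-period risk, gives a similar answer. An early leaver's AE probability is 1 − 0.30/0.357 = 0.159, so break-even is (0.300 − 0.159)/0.841, or about 17%, whatever share leaves.

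**The case against.** The strongest objection concerns direction. A reader might infer that the crude tables make mesalamine look less safe across the board. The documents do not support that. The AE definition in Protocol 8.1 can capture a relapse, and Protocol 8.2.2 names consequences of the underlying disease as an example when grading causality. Once roughly 17% to 25% of relapse withdrawals are recorded as AEs, the any-TEAE excess disappears, and above that placebo looks worse. AEs leading to discontinuation may well lean against placebo too. This objection stands, and it confines the directional claim to AEs other than UC worsening.

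Second, non-remission is not withdrawal. A subject can complete Month 6 and fail on symptoms or central endoscopy. The top of the range needs every non-remitter to leave early. This also stands.

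Third, the effect is small against sampling error. With 130 per arm and percentages near 35%, the standard error of a difference is √(2·0.35·0.65/130), or about 5.9 points, against a distortion of 0.9 to 4.3. The tables carry no test. Nor does the 2% rule for common TEAEs suffer much: 2% of 130 is 2.6 subjects, a 3% to 16% shift moves that by 0.08 to 0.42 of a subject, and either arm can qualify a term. All of this limits the importance, but the non-UC rows still lean one way.

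Fourth, a reader might infer that unequal exposure would be invisible. It would not: exposure and time to discontinuation are reported by arm, so a rough overall event rate could be formed. But SAP 8.1 stops at the last dose while the TEAE window runs to the end-of-treatment visit, and first-event rates by term could not be recovered from the summary tables. Protocol 8.5 does follow serious or related AEs, and takes in later related SAEs, but this does not extend the TEAE window.

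Finally, person-time rates have their own weakness. If intolerance occurs mainly early, longer exposure dilutes the mesalamine rate and could hide a real harm. That is a sound reason not to rest interpretation on adjusted rates alone.

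**Conclusion.** The gap is real but modest. Relapse forces withdrawal, the AE window then closes, and the planned AE tables take no account of time observed. For AEs other than UC worsening, crude figures can overstate mesalamine's relative AE burden, by about 1 to 4 points at a 40% AE risk. That size rests on four assumptions: mesalamine works as the sample size supposes, 25% to 100% of non-remitters leave early, withdrawal and AE hazards are constant, and the AE hazard is the same in both arms. If no non-remitter leaves early there is no bias. For any TEAE and for AEs leading to discontinuation the sign cannot be determined from the documents. This is a matter of reporting and interpreting descriptive safety tables, and the primary efficacy result is unaffected.

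**What to change.** Keep the crude percentages and event counts in SAP 10.2.1 and 10.2.2. For any TEAE, SAEs, ADRs, AEs leading to discontinuation and common TEAEs, add two rates by arm:

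- subjects with a first event per person-time, with time from first dose to the first event or, if none, to the end-of-treatment visit;
- events per person-time, with time from first dose to the end-of-treatment visit.

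Counting to that visit matches the TEAE definition in SAP 10.2; the last-dose endpoint in SAP 8.1 does not. Show the rates with and without UC-worsening terms, and list those terms before the blind is broken. Say that crude and person-time figures are to be read together, with neither as the sole basis for a between-arm statement.

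The cost is SAP wording and a few extra columns from dates already collected, with no change to trial conduct. The downside is that the rates assume a roughly constant hazard, which is why the crude percentages stay beside them.
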